## **Study Protocol**

### **Introduction**

Nearly 18% of United States adults meet criteria for alcohol dependence sometime in their lifetime, with only 24% of those individuals ever receiving any treatment for their disorder (Hasin et al., 2007). The pervasiveness of alcohol dependence indicates a need for continued development of high-impact treatments that are both effective and easily disseminated to a broad population. Recent evidence indicates that Episodic Future Thinking (EFT), the ability to self-project and pre-experience a future event, can help individuals to make changes to habitual behaviors, such as alcohol drinking (Snider et al., 2016). Here, we will evaluate the efficacy of EFT to help individuals reduce alcohol consumption. We anticipate that EFT will result in a reduction in alcohol consumption over a 2-week experimental period when compared to the control group.

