## **Procedures**

Study design. After the initial consent and assessment sessions, participants will be asked to provide daily self-report assessments of previous-day drinking over cell phone (see below) for 7 days with no other study intervention taking place. The purpose for this baseline period is to quantify baseline drinking patterns and ensure that the participant reliably responds to and conveys study information via cell phone. At the end

of this baseline period, participants who indicated adequate patterns of drinking and successfully reported their level of drinking as requested on baseline days will be invited to continue in the study. Participants will return to the laboratory to be provided with a SOBERLINK breathalyzer and be given instruction in its use.

Participants will be counterbalanced to either the active or control group based on alcohol use (e.g., average drinks per day). Both groups will be exposed to the same treatment events. The intervention period will last for 14 consecutive days, with three breathalyzer screens per day. During this 14-day period as they did during the baseline period, participants will self-report their previous-day alcohol use daily with a text message and/or phone call. Assessment sessions will be conducted prior to the intervention, immediately following the intervention, and at a 1-month follow-up.

Participants will be provided with a prepaid cell phone (if necessary) at the beginning of the study and a SOBERLINK breathalyzer at the beginning of the 14-day period, and receive a \$50 study completion bonus at the end of the study provided these devices are returned.

Cellular phone communication. All participants will either be allowed to use their own personal cell phone for study communications or receive a prepaid cell phone with service through a nationwide cell phone service provider that specializes in providing powerful usage controls with their cell phones, allowing us to restrict phone communication to a study phone and 911 service. If a participant chooses to use his or her personal cell phone for study communications and pays for text messages and/or phone calls on a per unit basis, we may reimburse the participant for the cost of those

messages and calls made for this study. We have used study-provided cell phones to facilitate study communication previously (Koffarnus et al., 2011).

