SOBERLINK breathalyzer monitoring. The SOBERLINK breathalyzer ([www.soberlink.net](http://www.soberlink.net)) contains a number of technological advances that make it ideally suited for remote breath samplings of alcohol use. To complete scheduled breathalyzer assessments, participants will simply blow into the device for 4 seconds. During the assessment, a picture is automatically taken of the user, which can be compared to a reference picture taken at study intake. The SOBERLINK device will automatically upload the breathalyzer results, the participant's location, and the picture of the user to a centralized, secure website where the data will be available to research staff. An on-screen display will notify participants of their blood alcohol content as indicated by expired Breath Alcohol Content (BrAC) as a percentage, and confirm submission if successful or instruct participants to redo the assessment if not successful for any reason (e.g., insufficient air flow to measure BrAC). Research staff will monitor these results and verify that the picture matches a reference picture for that participant.

All participants will be asked to complete breathalyzer screens 3 times per day for 14 days. A period of 14 days was chosen to determine if this procedure could result in alcoholic drink reduction using the EFT intervention. At the study onset, participants will be asked to designate the time at which each of the three breathalyzer screens will be scheduled each day. Participants will be asked to choose an assessment time shortly after they usually awaken, shortly before they go to bed at night, and one throughout the

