Daily alcohol use self-reports. Each day, participants will be asked to report how many alcoholic drinks they consumed the previous day (from the time they awoke to the time they fell asleep). We will ask them about the previous day alcohol use instead of the current day to best capture all drinks consumed each day without inconsistent response times complicating the measurement. Participants will be allowed to report this information at any time throughout the day, but will be encouraged through prompts to do so in the morning to increase the likelihood of accurate recall of previous day use. Participants will be allowed to report this information via text message or phone call. Participants will receive a reminder to report their previous-day drinking with text messages, followed by a phone call if they haven't contacted us by early evening. For completing this daily self-report, participants will receive \$1 in compensation.

Assessment sessions. Assessment sessions will be completed before the 14-day intervention period, immediately after the 14-day intervention period, and at a 1-month follow-up. Participants will complete a battery of questionnaires and tasks grouped into

three general categories: measures of substance use (including a urine test for drug and alcohol metabolites and a breath sample to test for recent alcohol use), clinically relevant measures including treatment acceptability, and measures of alcohol value and sensitivity.

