## **Participant Compensation**

Participants will receive

- \$15 compensation for the consent session
- \$15 for completion of assessment measures
- up to \$7 compensation for completion of the daily self-reports during the baseline period
- \$15 for completion of the pre-intervention (second) session
- 15 for the third session
- \$30 for the last follow-up assessment session
- up to \$56 for submission of the breathalyzer assessments and reports of previous-day drinking for the 14-day intervention
- \$50 for returning your SOBERLINK device and prepaid cell phone (if applicable)

These payments will be up to \$203 per participant, but may be less (depending on what study procedures he/she has completed).

To allow for payments that are both convenient and rapidly available, we will pay participants with reloadable prepaid cards through Greenphire ClinCard ([www.greenphire.com](http://www.greenphire.com)), an FDIC-insured payment provider that specializes in clinical trial stipend payments that comply with IRB privacy regulations and considerations. At

intake, each participant will receive a prepaid MasterCard debit card that can be used anywhere that accepts MasterCard. As payments are earned in the course of the study, additional funds will be added to the account for that participant. Funds are immediately available when added and participants can check their balance as desired. This system will allow frequent, immediately available payments without the burden of frequent laboratory visits that would negate some of the advantages of remote alcohol monitoring.

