RMET15-955 Episodic Thinking (ET) as a Candidate Technique to Reduce
Alcohol Consumption

Statistical Analysis Plan

10/26/2017

Statistical Analysis Plan

Descriptive statistics, chi-square, and t-test will be used to compare means and frequencies of sample characteristics among the two groups. Paired t-tests will be carried out to compare alcohol consumption, rates of discounting, alcohol valuation, PANAS measures, and craving scores before and after the intervention within groups. Discounting of delayed money will be assessed using an adjusting-delay task (Koffarnus and Bickel 2014) and an adjusting-amount task (see Du, Green, and Myerson 2002). Discount rate in both tasks will be calculated using the following hyperbolic equation, (Mazur 1987)

$$V = \frac{A}{1 + kD}$$

In this formula, V refers to the discounted value of a delayed reward; A represents the amount of the delayed reward; D equals the delay of the award; and k represents the delay-discounting rate (Mazur 1987). A higher k value means steeper discounting curve and reflects greater impulsivity, while lower k value means shallower discounting curve with less impulsivity. To provide an estimate of k , we will fit the hyperbolic equation to participants' indifference points (given in discounted monetary value), and use its natural log transformation in analyses. All the statistical analyses will be conducted using Prism 7 at a significance level of 0.05.

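### Do previous-day reports made during the 14-day intervention leave day 14 without a drink count?

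*Protocol*

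**What the plan says.** The Protocol's Introduction states the hypothesis over the whole intervention: "We anticipate that EFT will result in a reduction in alcohol consumption over a 2-week experimental period when compared to the control group". Under Procedures, the Study design paragraph sets the length and the screening schedule, "The intervention period will last for 14 consecutive days, with three breathalyzer screens per day", and then describes the reports: "During this 14-day period as they did during the baseline period, participants will self-report their previous-day alcohol use daily with a text message". The paragraph on daily self-reports defines what each one covers, "Each day, participants will be asked to report how many alcoholic drinks they consumed the previous day", counted from waking to falling asleep. It gives the reason: asking about a finished day captures all of that day's drinking.

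The paragraph on assessment sessions adds a visit straight after the intervention: "Assessment sessions will be completed before the 14-day intervention period, immediately after the 14-day intervention period, and at a 1-month follow-up". That visit includes measures of substance use, described only by general category.

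The Participant Compensation section sets a single cap of $56 for "submission of the breathalyzer assessments and reports of previous-day drinking for the 14-day intervention".

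The SAP says only "Paired t-tests will be carried out to compare alcohol consumption" (among other measures) before and after the intervention within groups. It does not say which dates make up either window.

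**The concern.** A previous-day diary always runs one day behind the calendar. If reporting starts on day 1 and stops on day 14, the first report describes a day before the intervention began, and the last day of the intervention is never described. The breath screens do run on day 14 ("All participants will be asked to complete breathalyzer screens 3 times per day for 14 days"), but they give a breath alcohol level and not a number of drinks. The visit that follows is not said to ask about day 14.

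The daily report is the only drink count the protocol describes for the two weeks in the hypothesis. An analyst who averaged all 14 reports would include a day before the intervention, pulling the estimated reduction towards zero. One who kept only days 1-13 would have an incomplete second week, with one weekday under-represented. Neither document says which to do.

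**Working it through.** **Inputs.** 14 days, three screens a day, $1 per screen, $1 per report, caps of $56 (intervention) and $7 (baseline), all from the Protocol (Procedures; Participant Compensation).

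**Reproducing the cap.** 14 × 3 × $1 + 14 × $1 = $42 + $14 = $56, as stated. The full list, 15 + 15 + 7 + 15 + 15 + 30 + 56 + 50, gives the stated $203. So 14 intervention reports are paid for; a 15th would make the cap $57.

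**Coverage.** A report on day d covers day d-1.

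| Reports made on | Days covered | Intervention days covered | Cap |
|---|---|---|---|
| 1-14 | 0-13 | 13 of 14 | $56 |
| 2-15 | 1-14 | 14 of 14 | $56 |

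The Study design sentence read literally gives the first row. The compensation wording, read as reports about those 14 days, gives the second. The cap fits both and cannot choose between them.

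**Baseline.** On the literal reading, the seven baseline reports also run a day behind: they cover the day before baseline and baseline days 1-6. That is still seven consecutive days without intervention, each weekday once, so the comparator remains a full week.

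**Dilution on the literal reading, all 14 reports averaged.** Let f be the share of a constant effect already present on day 0. The effect appears at (13 + f)/14 of its size:
- f = 0: 13/14 = 92.9%
- f = 0.5: 13.5/14 = 96.4%
- f = 1 (for example, cues already in use on the visit day): 100%

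Days 0-13 contain each weekday twice, so this average has no weekday imbalance.

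**Literal reading, reports dated to the day of drinking.** Days 1-13 remain and a constant effect is not diluted. One weekday has weight 1/13 (7.7%) and the other six 2/13 (15.4%), against 1/7 (14.3%). Assume two weekend days with x more drinks than weekdays; the documents give no figure, so take x from 1 to 4. The full-window excess is 4x/14.
- Weekend day lost: 3x/13 - 4x/14 = -0.055x, or -0.05 to -0.22 drinks/day.
- Weekday lost: 4x/13 - 4x/14 = +0.022x, or +0.02 to +0.09 drinks/day.

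These are shifts for one participant. With start days spread evenly over the week, their sum over the seven cases is 2 × (-0.05495x) + 5 × (+0.02198x) = 0.

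**If the effect is not constant.** Suppose it grew in proportion to the day number. The true mean over days 1-14 is 7.5 units. Averaging days 0-13 gives 91/14 = 6.5 (86.7%); days 1-13 give 91/13 = 7.0 (93.3%). The direction is still towards no effect.

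**The case for a change.** The strongest case for a change is textual. The Study design sentence is the only one that says when reports are made, and it puts them inside the 14 days. No section mentions a report on the morning after day 14, and the visit that follows names urine and breath tests but no drink count. Stating the dates would cost nothing: 14 paid reports on days 2-15 leave $56 and $203 unchanged.

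It is true that the calendar is unwritten and that the SAP leaves both windows undefined. It does not follow that day 14 is lost. The sentence describes a daily routine and does not set first and last report dates. The assessment battery is listed only by category, so an unnamed item cannot be taken as omitted. Staff are in contact with participants immediately after day 14, and the protocol's stated reason for asking about the previous day is to capture each day's drinking in full.

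One apparent repair would do more harm than the gap. Moving the day-0 report into the baseline mean would, if the periods are contiguous, give eight days with one weekday counted twice. The shift would be 3x/8 - 2x/7 = +0.089x or 2x/8 - 2x/7 = -0.036x, larger than the -0.055x or +0.022x it was meant to avoid.

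**Conclusion.** No change follows. The documents leave a routine detail unstated, and analysts can fill it sensibly by dating each report to the day it describes and leaving any day-0 report out of both windows. On one reasonable reading all 14 days are covered. On the other, one day in 14 (7.1%) has no daily report, and a constant effect is understated by at most 7.1% if all reports are averaged, or not at all if they are dated by drinking day.

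The report schedule is the same in both groups, so any dilution acts alike on both and cannot create a difference where none exists. The weekday shift cancels on average unless start days cluster, which the documents do not suggest.

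These sizes assume a constant effect and a weekend excess of 1 to 4 drinks. An effect that built steadily through the two weeks would be understated somewhat more, again towards no effect. The conclusion of the trial does not depend on this point.

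### The SAP plans no EFT-versus-ERT test of any outcome, so the protocol's between-group hypothesis goes untested; as a consequence the home breathalyzer screens enter no stated analysis, and the SAP is silent on the 1-month visit

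*Protocol*

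**What the plan says.** **Hypothesis.** The protocol's Introduction expects that "EFT will result in a reduction in alcohol consumption over a 2-week experimental period when compared to the control group". This is a contrast between arms, over the two-week period.

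**Assignment.** Protocol, Procedures (Study design): "Participants will be counterbalanced to either the active or control group based on alcohol use". Neither document says the assignment is random.

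**Drinking data.** Self-reported drinks are collected daily in a 7-day baseline period. During the 14 intervention days, "participants will self-report their previous-day alcohol use daily with a text message and/or phone call". For the home device, Procedures (SOBERLINK breathalyzer monitoring) says: "All participants will be asked to complete breathalyzer screens 3 times per day for 14 days". Participants receive "a SOBERLINK breathalyzer at the beginning of the 14-day period", so the baseline week has self-report only.

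**Visits.** Assessment sessions take place before the intervention, straight after it, and at 1 month.

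**Analysis.** The SAP has two sentences on tests. One uses descriptive statistics, chi-square and t-tests to "compare means and frequencies of sample characteristics among the two groups". The other applies paired t-tests to alcohol consumption, discounting, alcohol valuation, PANAS and "craving scores before and after the intervention within groups". The SAP does not mention the breathalyzer or the 1-month visit, and it does not say which measure represents alcohol consumption. It adds that "All the statistical analyses will be conducted using Prism 7", at the 0.05 level.

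**The concern.** The question the trial asks and the tests it plans do not match. A paired test inside the EFT arm asks whether EFT participants changed. It cannot separate an effect of EFT from change that both arms would show anyway. Such shared change is plausible here: everyone enrolled wants to quit or cut down, and both arms get the same monitoring, payments and contact. The ERT arm exists to absorb that change, and the SAP never uses it for this purpose.

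With no between-group test planned, a reader of the results is left to set one within-arm p-value against the other. One arm significant and the other not is easily read as evidence for EFT, although it is not a test of the difference.

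The same gap affects the screens. They are the only daily device-based measure of drinking and could support or qualify the self-reports. A between-group comparison can use them without a baseline value; a before-after test cannot. If they are analysed later, the BrAC cut-off and the handling of missing screens and failed photo matches could be chosen with results in view.

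**Working it through.** **1. The plan's own figure.** Screens per participant: 3 × 14 = 42. At 1 dollar per screen and 1 dollar per daily report, 42 + 14 = 56 dollars, the cap given under Participant Compensation. The count is confirmed.

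**2. Each data source against the SAP's tests.**

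| Data | Pre-intervention value? | Within-arm paired test possible? | Between-arm outcome test planned? |
|---|---|---|---|
| Self-reported drinks per day | Yes, 7-day baseline | Yes | No |
| Discounting, valuation, PANAS, craving | Before-after comparison planned in the SAP | Yes | No |
| Home breathalyzer screens | No, device issued at the start of the 14 days | No | No |
| 1-month visit | Yes, pre-intervention session | Possible, but not mentioned | No |

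The last column is empty of planned tests. The screens fall out for two reasons together: they have no before value, and no between-arm outcome test exists.

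**3. What two within-arm p-values can show.** Suppose both arms truly change by the same amount, the arms are independent, and each paired test rejects with probability p. Then

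P(exactly one arm significant) = 2p(1-p).

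- Neither arm changes, p = 0.05: 2 × 0.05 × 0.95 = 9.5%
- p = 0.50: 2 × 0.50 × 0.50 = 50%
- p = 0.80: 2 × 0.80 × 0.20 = 32%
- p = 0.98: 2 × 0.98 × 0.02 = 4% (3.9%)

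At p = 0.50 and 0.80, half of each figure (25% and 16%) is the pattern of EFT significant and ERT not.

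The documents give no effect size, so p is an assumption. To place it, take 100 per arm (the ceiling of 200 split equally), two-sided 0.05, and power ≈ Φ(d√n − 1.96), where d is the standardised within-arm change:

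- d = 0.2: Φ(2 − 1.96) = 0.52, so exactly one arm significant 50%
- d = 0.3: Φ(3 − 1.96) = 0.85, so 25%
- d = 0.4: Φ(4 − 1.96) = 0.98, so 4%

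The chance is large at intermediate power and small at very high power. At very high power both arms tend to be significant, which again says nothing about the difference between them.

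**4. What a direct comparison could detect.** For a two-sample test at 80% power, the detectable standardised difference is (1.96 + 0.84) × √(2/n). That is 0.40 at 100 per arm, 0.46 at 75 and 0.56 at 50. Equal arms are assumed. Since up to 200 enroll and only those who pass the baseline week continue, 100 per arm is an upper limit.

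**The case against.** **The screens may be for monitoring only.** Neither document names them as an efficacy outcome; staff are said to monitor the results, and the stated aim is fewer drinks. This stands. A reader might infer that the SAP dropped a planned breathalyzer endpoint, but the documents do not support that. On the other side, the protocol spaces the screens to improve detection, pays for each whatever its result, and checks identity by photograph. That justifies a supporting role and no more.

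**The SAP never says the arms will be judged by comparing p-values.** True. The calculation shows only that the planned output cannot be made to answer the hypothesis. It does not show that the sponsor intends that comparison.

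**The undefined terms may cover more.** 'Alcohol consumption' could include the breath and urine samples from the sessions, which do have a pre-intervention value. No reading gives the home screens one. 'After' could be stretched to the 1-month visit, but the SAP does not say so. Nor should 'after' be taken as the post-intervention session for every outcome, since that would exclude the daily reports made during the 14 days.

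**Screen rules are partly set.** The protocol gives a submission window and requires photo checks, so it would be wrong to say the window is undefined. Only the late limit (30 to 60 minutes), the BrAC cut-off, and the analytic handling of failed matches and missing screens are open. Nothing suggests that limits or submission rates differ between arms. With equal submission and the same missingness mechanism in both arms, neither way of treating missing screens creates a false gap when drinking is equal.

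**The vendor copy is deleted after data collection.** A reader might infer that the data would be lost. The Data Protection section describes vendor storage as additional to the study's own, so this does not follow.

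**Conclusion.** The concern holds. The hypothesis is between groups, and the SAP tests outcomes only within groups, so following it yields no EFT-versus-ERT estimate for any outcome. This rests on the text alone and needs no assumption. The SAP should be corrected.

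The 4% to 50% range for a misleading one-arm result is illustrative. It depends on equal true changes, independent arms and assumed within-arm power, none of which the documents give.

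The unused 42 screens follow from the main gap and are secondary to it. The silence on the 1-month visit is an omission in the SAP only; the protocol schedules the visit and pays 30 dollars for it.

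**What to change.** 1. **Main test.** Compare mean self-reported drinks per day over the 14 intervention days, EFT versus ERT, in a linear model adjusted for the baseline-week mean. Report the adjusted difference with its 95% confidence interval. Name the software if Prism 7 is not used; an unpaired t-test on change from baseline is the simple fallback. Keep the paired tests as descriptive.
2. **Screens, secondary and supporting.** Compare the per-participant proportion of alcohol-negative screens between arms, adjusted for baseline drinks per day. Fix in advance the BrAC cut-off, the handling of failed photo matches, and a single late limit within the protocol's 30 to 60 minutes. Report the result on submitted screens and again with missing screens counted as not negative, and show submission rates by arm.
3. **Time points.** Define 'after' by outcome: the 14-day period for daily drinks, and the immediate post-intervention session for discounting, valuation, PANAS and craving. Label any 1-month between-group comparison as secondary.
4. **Status.** If outcome data had already been seen when these analyses are added, label them post hoc.

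**Cost.** SAP wording and a few extra analyses of data the protocol already plans to collect, with possibly a second software package. One limit remains: assignment is described as counterbalanced on alcohol use and is not stated to be random, so adjustment does not guarantee comparable arms.
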